8.3.5.2. Cardiovascular Events

A summary of the number and percentage of subjects with cardiovascular events will be reported by treatment group and therapeutic phase.

A by-subject listing of all the data elements collected on the eCRF page will be presented for subjects who experience cardiovascular events.

8.3.5.3. Pancreatitis and Pancreatic Cancer

The number and percent of subjects with pancreatitis and pancreatic cancer will be reported by treatment group. A by-subject listing of all the data elements collected on pancreatitis event page of the eCRF will be presented for subjects who experienced pancreatitis and pancreatic cancer. This listing of the pancreatitis events will also include the adjudication results as determined by the independent pancreatitis adjudication committee.

8.3.5.4. Thyroid Adverse Events

The number and percent of subjects with thyroid AEs will be reported by treatment group. Additionally thyroid adverse events identified by a customized MedDRA query will be presented by treatment group.

A by-subject listing of all the data elements captured in the thyroid tumor eCRF page will be produced.

8.3.5.5. Gastrointestinal (GI) Events

A summary of the number and percentage of subjects with GI events (specifically, AEs coded to the MedDRA SOC of gastrointestinal disorders) will be reported by treatment group and therapeutic phase (pre-, on-, or post-therapy). Also, summaries of on-therapy GI events that lead to withdrawal of active treatment, treatment-related and serious GI events (including those that do not necessarily lead to withdrawal of active treatment) will be presented separately by treatment group.

For each subject, the time to first occurrence of a GI event is calculated as the number of days between the randomization date and the date of onset of the first on-therapy GI event plus 1. Subjects who do not experience any GI events will be censored at the last dose date plus 25 days in the albiglutide arm or within the last dose date in the lispro arm. The median time to first occurrence of a GI event as well as the Kaplan-Meier probability of first occurrence of a GI event at various time points will be presented for each treatment group. Kaplan-Meier curves for the time to first occurrence of a GI event for each treatment group will also be presented.

The prevalence of GI events will be reported and plotted by treatment group.

The number and percentage of subjects reporting nausea at each study week will be presented by treatment group. Each week will include those subjects with onset of nausea during that particular week and also those subjects with nausea that started during a previous week but has not resolved. The prevalence of nausea will also be plotted over time. Similar summaries and plots will be presented for subjects reporting events of diarrhea and also separately for subjects reporting events of vomiting. In addition, a combined summary and accompanying plot of the number and percentage of subjects reporting events of nausea and/or vomiting will be presented.

8.3.5.6. Systemic Allergic Reactions

Systemic allergic reactions are reported by the investigators on the eCRF. The number and percentage of subjects with suspected systemic allergic reactions will be presented by treatment group. In addition, the time to first occurrence of a systemic allergic reaction will be analyzed and presented in a manner identical to that described above for first occurrence of a GI event.

A summary of systemic allergic reactions based on customized MedDRA query (CMQ) list identified by GSK will also be presented. Analyses will be repeated for this data.

8.3.5.7. Injection Site Reactions

Injection site reactions are reported by the investigators on the eCRF. The number and percentage of subjects with injection site reactions will be presented. In addition, the time to first occurrence of an injection site reaction will be analyzed and presented in a manner identical to that described above for first occurrence of a GI event.

The number and percentage of subjects reporting injection site reactions at each study week will be presented by treatment group. Each week will include those subjects with

the onset of an injection site reaction during that particular week as well as those subjects with injection site reactions from previous weeks that have not resolved. The incidence of injection site reactions will be plotted over time. Various characteristics of injection site reactions at the event level and subject level will be summarized.

A by-subject listing of injection site reactions will also be produced.

8.3.5.8. Liver Events

The number and percentage of subjects with liver events that have been identified by investigators on the liver events eCRF page will be presented by treatment group. Additionally, liver events identified by a customized MedDRA query will also be presented by treatment group. By-subject listings of all the data elements collected on the eCRF page will be presented for subjects who experience adverse liver events, as identified by the investigators.

8.3.5.9. Atrial Fibrillation/Flutter

The number and percentage of subjects with Atrial Fibrillation/Flutter events will be presented by treatment group for Atrial Fibrillation and Atrial Flutter. By-subject listings of all the data elements collected on the Atrial Fibrillation and Atrial Flutter event eCRF page will be presented for subjects who experience atrial fibrillation/flutter events, as reported by the investigators.

8.3.5.10. Pneumonia

The number and percentage of subjects with Pneumonia events will be presented by treatment group for Pneumonia event reported by the investigator on the eCRF. Summary of Pneumonia events identified by a selected list of preferred terms will also be provided. By-subject listings of all the data elements collected on the Pneumonia event eCRF page will be presented for subjects who experience pneumonia events, as reported by the investigators.

8.3.5.11. Diabetic Retinopathy

The number and percentage of subjects with diabetic retinopathy events will be presented by treatment group. A by-subject listing of all the data elements collected on the diabetic retinopathy eCRF page will be presented for subjects who experience diabetic retinopathy, as reported by the investigators.

8.3.5.12. Appendicitis

The preferred terms containing the word “appendicitis” will be identified as Appendicitis events. The number and percentage of subjects with appendicitis will be presented by treatment group and a by-subject listing will be presented.

8.3.5.13. Malignant Neoplasm

Malignant neoplasm will be captured in the AE eCRF pages. The number and percentages of subjects with malignant neoplasm identified by a customized MedDRA query will be presented by treatment group and a by-subject listing will be presented.

8.3.6. Pregnancies

A listing of subject pregnancies will be provided.

8.3.7. Clinical Laboratory Evaluations

Laboratory results that are beyond the limits of quantification will have the inequality sign dropped ($<$, \leq , $>$, or \geq) and the quantification limit will be used as the numeric result for summarization.

8.3.7.1. Chemistry, Hematology and Urinalysis

Laboratory parameters include the following tests: hematology, chemistry and urinalysis. Established or generally acknowledged methods, normal ranges, and quality control procedures will be supplied by Quest Diagnostics Clinical Laboratory for the study records.

Hematology parameters used in summaries include complete blood count with red blood cell indices, white blood cell count differential, and platelet count. Chemistry parameters (including lipids) used in summaries include glucose, blood urea nitrogen, creatinine, sodium, potassium, chloride, carbon dioxide, calcium, total protein, albumin, total bilirubin, direct bilirubin, alkaline phosphatase (ALP), ALT, aspartate aminotransferase (AST), gamma-glutamyltransferase, uric acid, magnesium, phosphorus, eGFR, total cholesterol, low-density lipoprotein cholesterol, high-density lipoprotein cholesterol, triglycerides. Urinalysis parameters used in summaries include specific gravity, pH, glucose, ketones, microalbumin, creatinine, blood, leukocyte esterase, and nitrites.

All laboratory parameters will be summarized, for each treatment group, at every scheduled assessment time point using descriptive statistics and presented graphically. In addition, for hematology and chemistry laboratory parameters, change from Baseline in these quantitative tests will be summarized by treatment group and at every scheduled assessment postbaseline time point. Shift tables providing the number and percentage of subjects with indicated shifts (normal, abnormal not of clinical concern, abnormal of clinical concern) in their results from baseline to each scheduled postbaseline assessment will also be presented for all hematology and chemistry parameters.

Additionally, the number of subjects with laboratory values of potential clinical concern will be summarized by treatment group and scheduled assessment time point for hematology and chemistry. The criteria for laboratory values of potential clinical concern are detailed in [Appendix 7: Values of Potential Clinical Importance](#).

A summary of laboratory values of potential clinical concern will be provided for liver function tests, including ALT, AST, and total bilirubin. The criteria for liver function

tests of potential clinical concern are detailed in [Appendix 7: Values of Potential Clinical Importance](#).

All summaries will be done for the safety population and all laboratory data will be listed including hepatitis B, hepatitis C, fasting C-peptide, TSH, and urine pregnancy test results.

8.3.7.2. Albumin/Creatinine Ratio

The pattern of urine albumin to creatinine ratio (UACR) over time and change from Baseline over time will be evaluated descriptively using summary statistics and graphically at each scheduled visit. Change from Baseline of each of the ratios will be calculated as postbaseline value divided by baseline value. A value less than 1 represents a decrease from baseline and a value greater than one represents an increase from baseline. Shift tables providing the number and percentage of subjects with indicated shifts (normal, abnormal not of clinical concern, abnormal of clinical concern) in their results from baseline to each scheduled postbaseline assessment will also be presented.

The analysis will be performed on safety population and all data will be listed.

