8.3.5.2. Safety Analyses

Subject demographics, medical history, prior and concomitant medications, study medication exposure, vital sign measurements, clinical laboratory values, 12-lead ECG readings, physical examination assessments, and AE rates will be summarized by treatment group using descriptive statistics. For continuous variables, these summaries will include sample size, mean, median, standard deviation, minimum, and maximum. For categorical variables, the summaries will include frequencies and corresponding percentages. Some graphical summaries may be provided as well. No inferential testing will be performed on the safety variables.

For selected AEs of special interest, such as hypoglycemia, the exposure-adjusted incidence rate will also be calculated as the number of events in a given period divided by the total person time on treatment of subjects at risk within the same period. The exposure-adjusted incidence rate will be expressed as an annualized rate (expected number of events per 100 person-years).

Adverse events will be coded using MedDRA. Adverse events will be summarized in various subsets, including treatment-emergent AEs, related AEs, AEs leading to treatment discontinuation or withdrawal from study, SAEs, fatal AEs, etc. Adverse events will also be summarized by maximum intensity (mild, moderate, and severe).

Treatment-emergent AEs will be defined as any AEs, regardless of relationship to the investigational product, that occur after the first dose of the randomized study medication. Treatment-emergent AEs will also be further defined as on-therapy or post-therapy AEs for summary purposes.

Treatment-related AEs will be defined as any AEs that are considered by the investigator to be possibly, probably, or definitely related to the investigational product. In addition, if relationship information is missing, the AE will be considered treatment related.

Adverse events of special interest will also be summarized.

The number and percentage of subjects reporting specific events, such as specific GI events and injection site reactions, at each study week will be summarized and plotted over time. Characteristics of specific events, such as time to first occurrence, occurrence relative to preceding dose, and duration, will be summarized.

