11.5. Appendix 5: Derived and Transformed Data

11.5.1. Change from Baseline

The baseline value for an assessment is defined as the last available non-missing value prior to the first dose of the randomized treatment. Change from Baseline is defined as the postbaseline value minus the baseline value for the given assessment.

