3.131	Safety		On-therapy and Post-therapy Potential System Allergic Reactions Identified by the Investigator		
3.132	Safety		On-therapy and Post-therapy System Allergic Reactions Identified by a Customized MedDRA Query		
3.133	Safety		Kaplan-Meier Analysis of Time to First Occurrence of On-therapy Systemic Allergic Reaction Reported by the Investigator		

Safety : Tables					
No.	Population	IDSL / TST ID / Example Shell	Title	Programming Notes	Deliverable [Priority]
3.134	Safety		Kaplan-Meier Analysis of Time to First Occurrence of On-therapy Systemic Allergic Reaction Identified by a Customized MedDRA Query		
3.141	Safety		On-therapy and Post-therapy Injection Site Reactions		
3.142	Safety		Kaplan-Meier Analysis of Time to First Occurrence of On-therapy Injection Site Reaction		
3.143	Safety		On-therapy Injection Site Reaction Over Time		
3.144	Safety		Summary Characteristics of On-therapy Injection Site Reactions Identified by the Investigator		
3.151	Safety		On-therapy and Post-therapy Liver Events Identified by a Customized MedDRA Query		
3.161	Safety		On-therapy and Post-therapy Pancreatitis and Pancreatic Cancer		
3.162	Safety		On-therapy and Post-therapy Adjudicated Pancreatitis Events		
3.171	Safety		On-therapy and Post-therapy Atrial Fibrillation and Atrial Flutter Adverse Events		
3.181	Safety		On-therapy and Post-therapy Pneumonia Adverse Events Reported by the Investigator		
3.182	Safety		On-therapy and Post-therapy Pneumonia Adverse Events Identified by a Customized MedDRA Query		
3.191	Safety		On-therapy and Post-therapy Diabetic Retinopathy Adverse Events		
3.201	Safety		On-therapy and Post-therapy Appendicitis Adverse Events		
3.211	Safety		On-therapy and Post-therapy Malignant Neoplasm Adverse Events Identified by a Customized MedDRA Query		

Safety : Tables					
No.	Population	IDSL / TST ID / Example Shell	Title	Programming Notes	Deliverable [Priority]
Labs					
3.221	Safety		Change from Baseline in Hematology by Visit		
3.222	Safety		Change from Baseline in Chemistry by Visit		
3.223	Safety		Hematology Values of Clinical Concern by Visit		
3.224	Safety		Chemistry Values of Clinical Concern by Visit		
3.225	Safety		Liver Function Tests of Clinical Concern by Visit		
3.226	Safety		Shift in Hematology by Visit		
3.227	Safety		Shift in Chemistry by Visit		
3.228	Safety		Urinalysis by Visit		
3.229	Safety		Change from Baseline to Week 26 in Urine Albumin/Creatinine Ratio (mg/mmol)		

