11.14.7. Safety Figures

Safety : Figures					
No.	Population	IDSL / TST ID / Example Shell	Title	Programming Notes	Deliverable [Priority]
Adverse Events					
3.01	Safety		On-therapy Hypoglycemic Events Over Time		
3.11	Safety		On-therapy Gastrointestinal Adverse Events Over Time		
3.12	Safety		Kaplan-Meier Plot of Time to First Occurrence of a Gastrointestinal Adverse Event over Time		
3.13	Safety		On-therapy Nausea Over Time		
3.14	Safety		On-therapy Diarrhea Over Time		
3.15	Safety		On-therapy Vomiting Over Time		
3.16	Safety		On-therapy Nausea or Vomiting Over Time		
3.31	Safety		Kaplan-Meier Plot of Time to First Occurrence of a Systemic Allergic Reaction Reported by the Investigator		
3.32	Safety		Kaplan-Meier Plot of Time to First Occurrence of a Systemic Allergic Reaction Identified by a Customized MedDRA Query		
3.41	Safety		Kaplan-Meier Plot of Time to First Occurrence of an Injection Site Reaction		
3.42	Safety		On-therapy Injection Site Reaction Over Time		
Labs					
3.51	Safety		Line Graph of Mean (+/- SE) Results for Hematology Parameters		
3.52	Safety		Line Graph of Mean (+/- SE) Results for Chemistry Parameters		

Safety : Figures					
No.	Population	IDSL / TST ID / Example Shell	Title	Programming Notes	Deliverable [Priority]
3.53	Safety		Line Graph of Mean (+/- SE) Change from Baseline Results for Hematology Parameters		
3.54	Safety		Line Graph of Mean (+/- SE) Change from Baseline Results for Chemistry Parameters		
3.55	Safety		Line Graph of Mean (+/- SE) Urine Albumin/Creatinine Ratio		
3.56	Safety		Scatter Plot of Urine Albumin/Creatinine Ratio		
Vital Signs					
3.61	Safety		Line Graph of Mean (+/- SE) of Vital Sign Parameters		
3.62	Safety		Line Graph of Mean (+/- SE) Change from Baseline in Vital Sign Parameters		
ECGs					
3.71	Safety		Line Graph of Mean (+/- SE) ECG Results over Time		

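### The mean of the post/baseline albumin/creatinine ratio exceeds 1 when nothing changes, so that row of a descriptive safety table would suggest an increase in both arms

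*SAP*

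**What the plan says.** SAP section 8.3.7.2 gives UACR its own derivation: "Change from Baseline of each of the ratios will be calculated as postbaseline value divided by baseline value". It also gives the reading rule: "A value less than 1 represents a decrease from baseline and a value greater than one represents an increase from baseline". On the summary it says only that the values and their change "will be evaluated descriptively using summary statistics and graphically at each scheduled visit", with shift tables in addition. It does not name the arithmetic mean.

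The mean comes from protocol section 8.3.5.2, which covers clinical laboratory values: "For continuous variables, these summaries will include sample size, mean, median, standard deviation, minimum, and maximum". SAP section 6.4 uses the same list for continuous baseline variables. Neither document mentions a logarithm or geometric mean for UACR.

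Two other places bear on the derivation:

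- SAP section 11.5.1 states, without exception, that "Change from Baseline is defined as the postbaseline value minus the baseline value for the given assessment".
- SAP section 11.14.6 titles Table 3.229 "Change from Baseline to Week 26 in Urine Albumin/Creatinine Ratio (mg/mmol", closing with that unit.

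The other UACR displays are shift Table 3.230, Figure 3.55 ("Line Graph of Mean (+/- SE) Urine Albumin/Creatinine Ratio"), scatter plot Figure 3.56 and Listing 160.

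**The concern.** The rule that 1 separates a decrease from an increase is right for a single subject, and for the median or geometric mean of many subjects. It is wrong for the arithmetic mean. A doubling (2.0) and a halving (0.5) cancel, yet they average 1.25. If the mean row is read by the SAP's own rule, both arms would seem to show rising albuminuria when nothing had happened. The median beside it would stay near 1, and the plan does not say which to read.

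A second difficulty is that the plan gives two definitions of change. A programmer following section 8.3.7.2 would compute a unitless ratio. One following section 11.5.1 and the title of Table 3.229 would compute a difference in mg/mmol.

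**Working it through.** The plan states no UACR variance, expected ratio or sample size, so it has no figure of its own to reproduce.

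**Inputs.** From the documents: change = post/baseline with reference value 1 (SAP 8.3.7.2); mean and median both reported (protocol 8.3.5.2); about 337 completers per arm (SAP 11.12), used only to size a simulation. Assumed: within-subject CV, shown as a range.

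**Direction, without a distribution.** Let B be baseline and P post. If nothing changes and the two are exchangeable, P/B and B/P have the same expectation, so

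E[P/B] = E[(P/B + B/P)/2] ≥ 1,

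because (r + 1/r)/2 ≥ 1 for every r > 0. Equality requires P = B in every subject.

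**Size, assuming log-normal variation.** Let B and P vary independently about the subject's own level with log-SD s. The log ratio then has mean 0 and variance 2s², so E[P/B] = exp(s²). As CV² = exp(s²) − 1, this equals 1 + CV². The median and geometric mean of the ratio are both 1.

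| Assumed CV | 1 + CV² |
|---|---|
| 20% | 1.04 |
| 30% | 1.09 |
| 40% | 1.16 |
| 50% | 1.25 |
| 60% | 1.36 |
| 80% | 1.64 |
| 100% | 2.00 |

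**Simulation check.** Two arms of 337, no true change, 1000 runs at each CV:

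- Both arms' arithmetic means exceeded 1 in 98% of runs at CV 20% and in 100% at CV 30% or more.
- The geometric mean averaged 0.999 to 1.002.
- The median averaged 0.999 to 1.004.
- The between-arm difference in arithmetic means averaged −0.012 to 0.001, consistent with its expected value of 0.

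**Can a real fall be hidden?** Take a true 20% fall. The expected mean ratio is 0.80 × exp(s²):

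- s = 0.3: 0.80 × 1.094 = 0.88
- s = 0.4: 0.80 × 1.174 = 0.94
- s = 0.5: 0.80 × 1.284 = 1.03

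The result reaches 1 when 1 + CV² = 1/0.80 = 1.25, that is at CV 50% (s about 0.47).

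**The case against.** The strongest reply is that little depends on this row. Section 8.3.7.2 never names the mean, and the protocol list that brings it in also requires the median, which stays at about 1. The table shells are in a separate document (SAP 11.14.2), so the rows of Table 3.229 cannot be checked. If that table holds a difference, as section 11.5.1 and the unit suggest, the ratio bias does not arise. Protocol section 8.3.5.2 also rules out inferential testing of safety variables, and UACR is not a primary, key secondary or exploratory endpoint.

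Most of this stands, and it limits the impact. It does not make the mean row right if section 8.3.7.2 is followed, and uncertainty over which quantity is tabulated is itself a defect.

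A reader might infer more than the documents support:

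- **That the renal displays as a whole would show worsening.** They would not. Table 3.230 uses categories, Figure 3.56 is a scatter plot, and the median ratio is unbiased.
- **That Figure 3.55 has the same bias.** It plots UACR levels, not the change ratio. With no change, the expected mean level is the same at baseline and Week 26. Skew can make that mean noisy but does not push it upward.
- **That the arms would be compared unfairly.** With equal variability, both means are inflated by the same factor.
- **That a true fall would be hidden.** For a 20% fall this needs a within-subject CV of about 50% or more, and the documents give no value.

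**Conclusion.** The point holds, and it is minor. As written, the plan reports an arithmetic mean of post/baseline ratios against a rule that treats 1 as no change. That mean exceeds 1 under no change whenever values vary within subjects. The direction needs only exchangeability of baseline and post values. The size (about 1.09 at CV 30%, 1.25 at 50%, 1.36 at 60%) rests on independent log-normal variation and an assumed CV.

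The effect is confined to the mean, with its SD, in one descriptive safety summary. No test or trial conclusion depends on it. The conflict between SAP section 8.3.7.2, section 11.5.1 and the unit in Table 3.229 needs no assumption and should be settled first.

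**What to change.** 1. In SAP 8.3.7.2, confirm that the ratio is what is tabulated. In section 11.5.1, state that the difference definition does not apply to UACR.
2. Summarise log(post) − log(baseline). Report the back-transformed geometric mean ratio to baseline with the median and quartiles; a 95% confidence interval is optional. Apply the below-1/above-1 rule to the geometric mean ratio and the median.
3. In Table 3.229, keep mg/mmol for the values only and remove it from the ratio.
4. Optionally, plot geometric means in Figure 3.55, to deal with skew only.

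SAP section 8.3.7 already replaces results beyond a quantification limit with the limit, so censored results remain usable on the log scale. The cost is a few lines of SAP text and a log transformation in one table, plus one figure if the option is taken. No new data are needed.
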